8.2 Baseline characterisation

Data preparation and exploratory analysis will include the investigation of potential outliers and missing data for all variables. Plots will be produced for all explanatory and outcome variables. For variables measured on the interval or ratio scale, these will include:

- Frequency plots to illustrate the distribution of the variable and whether categorisation may be necessary (for example, if heavily skewed)
- Box plots to illustrate the location and spread of the variable and identify potential outliers

For categorical variables, bar plots will be produced to illustrate distributions and highlight differences between exposure groups.

Skewed data will be transformed or categorised, as appropriate.

8.2.1 Summary statistics

Summary statistics will be produced for all baseline and outcome variables, as a complete dataset, by treatment group and for sub-groups. For variables measured on the interval or ratio scale, these will include:

- Sample size (n)
- Percentage non-missing
- Mean
- Standard Deviation (SD)
- Median
- Inter-quartile range (IQR – 25th and 75th percentiles)

For categorical variables, the summary statistics will include:

- Sample size (n)
- Count and percentage by category

Variables measured on the interval/ratio scale will be compared using a t-test (normal distribution) or Mann-Whitney U test (non-parametric). Categorical variables will be compared using a chi-square test. The statistical significance for all tests will be set at $p < 0.05$.

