8.0 Statistical analysis

8.1 Software used and power calculation

The dataset will be analysed using SPSS version 23, SAS version 9.3, Stata SE version 14 (StataCorp, College Station, TX) and Microsoft Office EXCEL 2013, as appropriate.

The study was powered using the occurrence of oral thrush as the representative adverse event. The occurrence of adverse events is 34% based on the oropharyngeal side effects in users of ICS in a real life setting reported in the literature¹³.

The minimum study numbers are based on the following assumption:

When the sample sizes in the groups are 293 and 147, a two-group large-sample normal approximation test of proportions with a one-sided 0.025 significance level will have 80% power to reject the null hypothesis that the test and the standard are not equivalent (the difference in proportions, $p_T - p_S$, is 0.130 or farther from zero in the same direction) in favor of the alternative hypothesis that the proportions in the two groups are equivalent, assuming that the expected difference in proportions is 0.000 and the proportion in the standard group is 0.300.

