8.3 Matching

Initially, baseline data will be compared between unmatched cohorts. Exact matching for categorical variables and coarsened exact matching for numeric variables will be used to match patients using 1:1 nearest neighbour matching, without replacement. Matching variables such as demographic data, disease co-morbidity and indicators of disease severity will be considered for selection using a combination of baseline data analysis and predictive modelling of the baseline data in relation to the primary outcome variable (independently of treatment group).

If patient numbers allow, patients will be matched on sub groups for age (under 16s and 16-65 year olds) and high/low average ICS dose (1000 µg non-extrafine beclomethasone dipropionate or more/under 1000 µg non-extrafine beclomethasone dipropionate). For the sub-question of step down patients, matching will be implemented if the numbers are sufficient.

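### Baseline comparability of the spacer groups is formally judged only by p<0.05 tests, which depend on sample size and at 293 v 147 miss a true 0.2-SD imbalance about half the time; standardised differences should replace them.

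*Protocol*

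**What the plan says.** Protocol section 8.2.1 (Summary statistics) prescribes a t-test or Mann-Whitney U test for interval and ratio variables. For the rest, "Categorical variables will be compared using a chi-square test. The statistical significance for all tests will be set at" p<0.05. The baseline mock tables in Appendix 2 set Volumatic beside Aerochamber and add one comparison column, the p-value.

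Section 8.3 (Matching) begins: "Initially, baseline data will be compared between unmatched cohorts". Matching variables are then considered "for selection using a combination of baseline data analysis and predictive modelling of the baseline data in relation to the primary outcome variable", with that modelling done without regard to treatment group. Matching is 1:1 and without replacement.

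Section 8.4.1 adjusts the primary conditional Poisson model for potential baseline confounders, which it does not name. The document gives no standardised difference and no criterion for balance after matching.

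**The concern.** This is a non-randomised comparison, so the primary conclusion depends on how well matching and adjustment remove differences between the spacer groups. A significance test is a poor guide to that. Its result mixes the size of the imbalance with the number of patients, so a non-significant result in a modest cohort is not evidence of balance, and a significant one in a large cohort need not matter.

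The questionnaire cohort may be only a few hundred patients, while the database cohort may be much larger, so one rule would act as two different standards. In the primary analysis, a residual imbalance that favours Aerochamber makes a false non-inferiority claim more likely. An imbalance in the other direction makes a true claim harder to reach.

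**Working it through.** **Inputs from the protocol.** Group sizes 293 and 147, described as minimum numbers; one-sided 0.025 level; 80% power; margin 0.130; both proportions 0.300 (all section 8.1). Baseline tests at p<0.05, taken as two-sided (8.2.1).

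**Assumptions, not in the protocol.** Imbalances of 0.1 to 0.3 SD; 10 points of event risk per SD of the covariate; 2,000 per group as an example of a larger database cohort.

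**1. The plan's own figure.** Power = Phi(0.13 / sqrt(0.3 x 0.7 x (1/293 + 1/147)) - 1.96) = Phi(0.13/0.0463 - 1.96) = 80.1%. The stated 80% is reproduced.

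**2. Miss rate of the baseline test.** The standard error of a standardised difference at 293 v 147 is sqrt(1/293 + 1/147) = 0.1011. The smallest observed difference that reaches p<0.05 is therefore 1.96 x 0.1011 = 0.198 SD. From the noncentral t distribution:

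| True imbalance | Missed at 293 v 147 |
|---|---|
| 0.1 SD | 83% |
| 0.2 SD | 49% |
| 0.3 SD | 16% |

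For 0.2 SD the Mann-Whitney test misses 51%, and the chi-square test misses 47-50% for binary covariates with the same standardised difference. Reaching 80% power for 0.2 SD would need 393 per group at 1:1.

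**3. Dependence on size.** A 0.1-SD difference is flagged 17% of the time at 293 v 147 and 88.5% of the time at 2,000 per group. The imbalance is the same and the verdict is opposite.

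**4. What a miss leaves in the sample.** A missed imbalance must be observed below 0.198 SD, so the full true value cannot be carried forward as bias. The mean observed imbalance given a miss is d - SE x phi((c - d)/SE) / P(miss), with c = 0.198 (the lower tail is negligible):
- d = 0.2: 0.2 - 0.1011 x 0.399/0.492 = 0.12 SD.
- d = 0.3: 0.3 - 0.1011 x 0.240/0.157 = 0.15 SD.

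The same calculation at 147 v 147 gives at most 0.16 SD.

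**5. Effect on the primary claim.** Take a true difference at the margin (43% v 30%) and 147 per arm after 1:1 matching. SE = sqrt((0.43 x 0.57 + 0.30 x 0.70)/147) = 0.0556. False non-inferiority = Phi(bias/SE - 1.96), where bias is 0.10 times the imbalance:
- no bias: 2.5%;
- 0.12 SD, bias 0.012: Phi(0.216 - 1.96) = 4.1%;
- 0.16 SD, bias 0.016: Phi(0.288 - 1.96) = 4.7%.

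The rise is from 2.5% to about 4-5%, for one covariate that is neither matched nor adjusted for.

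**The case against.** The strongest reply is that no passage turns the p-value into a decision rule. Section 8.3 says variables will be considered, without citing p<0.05, and 8.4.1 applies no significance criterion to its confounders. That the baseline data analysis of 8.3 includes the tests of 8.2.1 is an inference. It is a fair one, because those tests are the only formal between-group comparison of baseline data. They are not the only information: section 8.2 plans plots by exposure group, and the mock tables show means and SDs by arm, from which a reader could work out the standardised difference of a continuous variable.

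Outcome modelling is also a real second route. Ten points per SD at a 30% event rate is an odds ratio of about exp(0.10/(0.3 x 0.7)) = 1.6. In simulation, a univariable logistic model in 293 + 147 = 440 patients detected 1.61 per SD 99% of the time. Unless a variable must pass both screens, which 8.3 does not say, a confounder that strong would normally be kept. An odds ratio of 1.25 was detected only 56% of the time, but a full 0.2-SD imbalance in such a variable shifts the difference by just 0.9 points. This objection stands and limits the harm.

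It can also be said that balance diagnostics belong in the analysis plan. That would hold if the protocol were silent. Here it names a measure and builds it into the tables.

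**Conclusion.** The point holds as a weakness of method with moderate consequences. The protocol fixes a sample-size-dependent measure as its only formal baseline comparison, and at its own minimum sizes that measure misses a true 0.2-SD imbalance about 49% of the time. Larger cohorts would miss less, which is the same defect seen from the other side.

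Three stronger readings are tempting and not supported:
- **Non-significant variables are declared balanced and excluded.** The text does not say so.
- **Miss rates of 60% (0.2 SD) and 27% (0.3 SD) at 147 v 147.** These presume significance tests used as a balance check after matching. Section 8.3 places the comparison in the unmatched cohorts.
- **False non-inferiority of 5.5-7.8%.** This applies the full 0.2-0.3 SD as bias, although an imbalance that escapes the test averages only 0.12-0.16 SD in the sample.

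The 4-5% figure itself rests on an omitted variable, 10 points of risk per SD, a direction favouring Aerochamber and a true difference exactly at the margin. It illustrates the risk and does not predict the result. Several omitted covariates acting together could do more.

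**What to change.** - **8.2.1 and the baseline mock tables:** replace the p-value with the standardised mean difference, reported before and after matching.
- **8.3:** choose matching variables by prior knowledge and association with the outcome, and judge imbalance by the standardised difference instead of p<0.05.
- **8.4:** adjust for prognostic variables whose absolute standardised difference stays above a prespecified threshold after matching. A value of 0.10 is offered as an example; it does not come from the protocol.

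The cost is a change of wording and one recalculated table column. The small downside is that a few more covariates may enter the matching or the model. The change should be made before the matching set is chosen.

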8.3 Matching

Initially, baseline data will be compared between unmatched cohorts. Exact matching for categorical variables and coarsened exact matching for numeric variables will be used to match patients using 1:1 nearest neighbour matching, without replacement. Matching variables such as demographic data, disease co-morbidity and indicators of disease severity will be considered for selection using a combination of baseline data analysis and predictive modelling of the baseline data in relation to the primary outcome variable (independently of treatment group).

If patient numbers allow, patients will be matched on sub groups for age (under 16s and 16-65 year olds) and high/low average ICS dose (1000 µg non-extrafine beclomethasone dipropionate or more/under 1000 µg non-extrafine beclomethasone dipropionate). For the sub-question of step down patients, matching will be implemented if the numbers are sufficient.

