MDI	Able spacer	Aerochamber Plus	Optichamber	Pocket Chamber	Volumatic
Beclomethasone Dipropionate (Clenil Modulite)	a	a	a	a	✓
Beclomethasone Dipropionate HFA	a	✓	a	a	✗
Fluticasone propionate	a	✓	a	a	✓
Ciclesonide	a	✓	a	a	✗
Beclomethasone/ formoterol	a	✓	a	a	✗
Fluticasone propionate / formoterol	a	✓	a	a	✗
Fluticasone propionate / salmeterol	a	✓	a	a	✓

Table 2: Spacer and suitable MDI devices

a = fits spacer but not licensed for use ✓ = licensed for use ✗ = does not fit spacer

The license for non-extrafine beclomethasone dipropionate (Clenil Modulite) with the Volumatic spacer, but it has also been shown to be prescribed off-license for Aerochamber, in previous unpublished research from OPRI (formerly Research in Real Life). There is a concern that the use of some spacers may result in a greater number of adverse events; larger spacers such as the Volumatic[®] spacer have been shown to feature a lower deposition of drug on the filters compared to the use of smaller spacers and thus less more effective distribution².

In real-life practice, the effectiveness of any device combination depends on the willingness and ability of the patient to use it⁷. Patients may not use the spacers correctly in a number of ways as described in Table 3:

Errors with spacer devices
Placement of inhaler in the wrong end of the spacer
Failure to exhale slowly
Failure to shake inhaler well
Waiting too long before inhaling
Pressing too many times on the MDI
Rapid inhalation

Exhaling into device
Inadequate breath hold

Table 3: Spacer errors ⁷

In addition, primary care physicians who prescribe spacers may not adhere to prescription guidelines given that their patients may be unwilling to carry or use the devices.

In stage 1 of this study, a significant number of patients prescribed spacers and non-extra-fine beclomethasone dipropionate off license were found. Stage 2 will focus on comparing the adverse events between non-extra-fine beclomethasone dipropionate prescribed using the Volumatic[®] spacer and the Aerochamber[®] spacer.

For this study, database outcomes and patient questionnaires will be examined. Asthma questionnaires have been used in quality of life reviews⁸, randomised controlled trials⁹ and have been an essential component for improving asthma care in the United Kingdom ¹⁰.

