4.2 Study objectives

4.2.1 Primary objective

Non-inferiority of non-extrafine beclomethasone dipropionate with Aerochamber[®] spacer compared to non-extrafine beclomethasone dipropionate with Volumatic[®] spacer, in terms of the rate of patient-reported outcomes listed on the British Lung Foundation Questionnaire, ie the incidence of oral thrush or hoarseness.

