7.1 Demographic and baseline variables for patient questionnaire outcomes

- Gender (male/female)

- Age of patient (years, at index date)
- Body Mass Index (BMI, at time nearest index date, calculated from height and weight data if available, otherwise taken from practice-recorded BMI value, detailed definition in Appendix 1)
- Smoking status (identified by Read code, closest to index date)
- SABA daily dose calculated 1 year prior to index date*
- Percentage predicted peak flow (closest to index date)
- Total cumulative ICS dose
- Spacer type
- Total cumulative non-extrafine beclomethasone dipropionate therapy
- Duration of ICS therapy
- Number of exacerbations (ATS/ERS 2015 consensus definition[†]) from 1 year prior to index date
- Number of oral corticosteroid prescriptions from 1 year prior to index date
- Number of antibiotic prescriptions for lower respiratory tract infections from 1 year prior to index date
- History of comorbidities related to asthma:
 - Pneumonia (Read code diagnosis from 1 year prior to the index date)
 - Diabetes (Read code diagnosis and/or antidiabetic drugs ever prior to the index date)
 - Ischaemic heart disease (Read code diagnosis before one year prior to the index date)
 - Rhinitis (Read code diagnosis, including chronic and allergic rhinitis and prescriptions for nasal steroids between one year prior to index date)
 - Eczema (Read code diagnosis between one year prior to index date)
 - Osteoporosis (Read code diagnosis between one year prior to the index date)
 - Charlson Comorbidity Index (based on Read code diagnoses between one year prior to index date, detailed definition in Appendix 1)

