8.4 Analysis of study outcomes

8.4.1 Primary analysis: Questionnaire based adverse events

Adverse events as total and individual events in the questionnaires will be compared using a conditional Poisson regression model. The model will use empirical standard errors and adjustments will be made for potential baseline confounders.

The adjusted rate ratio with 95% confidence interval will be reported.

Non-inferiority in patient reported adverse events (oral thrush OR hoarseness) will be achieved if the proportion of Clenil/Aerochamber is no more than 13% higher (based on the upper boundary of the 95% confidence interval) than the proportion of patients on Clenil/Volumatic.¹⁴

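### Prior oral thrush and hoarseness are not named among the baseline variables that feed matching and adjustment, although they make up the primary endpoint; an imbalance would bias the non-inferiority result in a direction the protocol cannot show

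*Protocol*

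**What the plan says.** The primary objective (4.2.1) concerns questionnaire-reported side effects, "ie the incidence of oral thrush or hoarseness". Section 8.4.1 sets the rule: "Non-inferiority in patient reported adverse events (oral thrush OR hoarseness) will be achieved" if the upper 95% confidence limit for Aerochamber is no more than 13% above Volumatic. The answers are collected at the index date, which is the questionnaire date (5.2). The spacer must have been prescribed earlier, with no stated look-back limit (6.1).

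Confounding is handled in two places. Section 8.3 says that "Matching variables such as demographic data, disease co-morbidity and indicators of disease severity will be considered for selection", using the baseline data and a predictive model for the primary outcome that ignores treatment group. Section 8.4.1 adds adjustment for baseline confounders that it does not name.

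The baseline variables are itemised in 7.1 (questionnaire cohort) and 7.2 (database cohort). Under "History of comorbidities related to asthma" section 7.1 has pneumonia, diabetes, ischaemic heart disease, rhinitis, eczema, osteoporosis and the Charlson index; 7.2 has the same conditions. Elsewhere the lists cover demographics, smoking, steroid dose and duration, SABA dose, exacerbations, oral steroid and antibiotic prescriptions, and peak flow. Neither list, nor the mock baseline tables in Appendix 2, includes a history of a local steroid side effect. Thrush and hoarseness appear only as outcomes (7.3 and, for thrush, 7.4).

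**The concern.** In a non-randomised comparison, a patient's earlier experience of the endpoint condition is an obvious candidate confounder. It can plausibly predict a later report, and it can plausibly influence which device is prescribed. Section 3.0 gives some reason to think device choice could respond to it: it says a spacer's fine mist is less likely to deposit in the oropharynx, and that "There is a concern that the use of some spacers may result in a greater number of adverse events". It also notes that Volumatic is the licensed spacer for this product.

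If the history is unevenly spread, the two groups would report thrush or hoarseness at different rates even with identical devices. The primary conclusion is then exposed to an error in either direction, and the modelling step in 8.3 cannot pick a variable that is not in the data it works on.

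**Working it through.** **Where the variable could enter.**
- Sections 7.1 and 7.2: not listed.
- Section 8.3: the wording is open, but selection runs on the baseline data.
- Section 8.4.1: the confounders are unnamed.
- Section 6.3: the study dataset holds only variables needed for the study objectives, so an unlisted variable may not be extracted.
- Section 13.0: extraction is planned for 10 November 2016; the protocol is dated 28 October 2016.
- The plan already does this for another outcome: osteoporosis is a baseline variable (7.1, 7.2) and a database outcome (7.4).

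**The plan's own figure.** Inputs from 8.1: "When the sample sizes in the groups are 293 and 147"; "one-sided 0.025 significance level will have 80% power"; the margin, where the difference "is 0.130 or farther from zero in the same direction"; expected proportion 0.300 in both groups.
- SE = sqrt(0.30 × 0.70 × (1/147 + 1/293)) = 0.0463
- Power = Φ(0.13/0.0463 − 1.96) = Φ(0.847) = 0.801

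The stated 80% reproduces. It assumes no confounding.

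**Bias.** For a binary history with no true device effect:

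bias = (difference between groups in prevalence of history) × (endpoint risk with history − endpoint risk without)

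The protocol gives neither factor. Both are assumptions, and the formula takes no credit for listed variables that correlate with the history.

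| Assumed imbalance | Assumed risk gap | Bias | Share of 0.13 margin |
|---|---|---|---|
| 0.10 | 0.25 | 0.025 | 0.025/0.13 = 19% |
| 0.15 | 0.25 | 0.0375 | 0.0375/0.13 = 29% |
| 0.20 | 0.40 | 0.080 | 0.080/0.13 = 62% |

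The middle row in full: suppose 30% of one group and 15% of the other have the history, with risk 50% with it and 25% without. The rates are 0.30 × 0.50 + 0.70 × 0.25 = 0.325 and 0.15 × 0.50 + 0.85 × 0.25 = 0.2875, a gap of 0.0375 with no device effect.

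**Effect on the decision.** I use 147 Volumatic and 293 Aerochamber patients; section 8.1 does not say which group is which, and swapping them changes the results by less than one percentage point. The 13% in 8.4.1 is read as a difference in proportions, as in 8.1. The probability of declaring non-inferiority is Φ((0.13 − expected observed difference)/SE − 1.96), with unpooled SE.

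- *History mainly on Volumatic, true Aerochamber excess equal to the margin.* Aerochamber is 0.43 and Volumatic 0.30 + bias.
  - No bias: 0.025.
  - Bias 0.025: SE = sqrt(0.325 × 0.675/147 + 0.43 × 0.57/293) = 0.0483; Φ(0.025/0.0483 − 1.96) = Φ(−1.44) = 0.075.
  - Bias 0.04: 0.128.
  - Bias 0.08: SE = 0.0494; Φ(−0.34) = 0.367.
- *History mainly on Aerochamber, true difference zero.* Volumatic is 0.30 and Aerochamber 0.30 + bias.
  - No bias: power 0.801.
  - Bias 0.025: SE = 0.0467; Φ(0.105/0.0467 − 1.96) = Φ(0.29) = 0.61.
  - Bias 0.04: 0.485.
  - Bias 0.08: 0.184.

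**The case against.** The strongest reply is that the plan does not exclude the variable. The matching wording is illustrative, the model confounders are left general, and a final covariate set is often settled in a statistical analysis plan. That stands as far as it goes: the variable is unnamed, not barred, and the lists are not declared exhaustive. It does not dispose of the point, because the protocol itself itemises the baseline data that selection works on, and 6.3 restricts what is extracted.

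A reader might infer that patients with earlier local side effects were steered to Volumatic, so that the study is set up to find non-inferiority. The documents do not support that. Every patient in both groups has a spacer, so a general reason for using one creates no imbalance. The reasons given in 3.0 are childhood, poor co-ordination, high steroid dose, older age, and dental or mouth problems; earlier thrush or hoarseness is not among them. The stated worry about some spacers is not said to drive prescribing.

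A reader might also infer that this history is the strongest predictor of the endpoint. That is clinical judgement and has no figure in the protocol. Listed variables such as cumulative steroid dose, duration of therapy, smoking and diabetes may act as partial proxies, as may the high/low dose matching planned if numbers allow.

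Finally, the history may be only partly recoverable. Hoarseness is not among the Read-coded outcomes in 7.4, and section 3.0 itself says some side effects are seldom coded. Section 6.1 requires two years of records before the questionnaire, which may not reach back before the spacer. This stands, and it shapes the remedy.

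**Conclusion.** The gap is real and worth closing. Its size is conditional: 2.5 to 8 points of bias, under assumed factors that the protocol neither supports nor rules out. With bias towards Volumatic, the chance of wrongly declaring non-inferiority at the margin rises from 2.5% to roughly 7% to 37%. With bias towards Aerochamber, power falls from 80% to roughly 61% to 18%. The direction is unknown, so the supportable conclusion is that the primary result is open to avoidable confounding, not that it is tilted towards success. This is a low-cost improvement to the plan and does not by itself invalidate the design.

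**What to change.** Add to 7.1 and 7.2: *oral thrush (Read code and/or oral antifungal prescription) and, where coded, hoarseness, recorded before the first spacer prescription.* Make it a candidate matching variable in 8.3 or, preferably, a mandatory covariate in the 8.4.1 model.

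The timing matters. In the questionnaire cohort the baseline year ends at the questionnaire, so events in that year may already result from the spacer, and adjusting for them could remove a real device effect. In the database cohort the index date is the spacer prescription (5.4), so the one-year baseline precedes that prescription.

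For questionnaire patients whose records do not reach back before the first spacer, code the history as unknown rather than absent. Add a sensitivity analysis restricted to patients with an observable pre-spacer period.

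Cost: a code list and one or two derived variables, specified before extraction. Capture will be incomplete, especially for hoarseness, so some residual confounding will remain. Exact matching on the variable would lose some pairs; using it as a covariate avoids that loss but still has to handle the unknown category.

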5.2 Study design (questionnaire outcomes)

A longitudinal study to compare patient-reported side effects for asthma patients prescribed non extra fine beclomethasone with Volumatic[®] spacer or Aerochamber[®] spacer (Figure 4). The index date of the study is the date of administration of the BLF Questionnaire. This study design will also be used to explore patients who step down at the index date with Volumatic and Aerochamber spacers. This exploratory objective will explore the baseline year (ie: year before index) in terms of comparative efficacy. If required (due to insufficient patients) an additional study design will be incorporated which will consider date of step down as index date (instead of date of BLF questionnaire).

[figure not shown]

Figure 4: Study Design (questionnaire outcomes)

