5.4 Study design (database outcomes)

This is a historical database study composed of a 1-year baseline period for demographics, characterisation and matching. The index date is the date of prescription of a spacer (Volumatic[®] or Aerochamber[®]), with a 3-year outcome period for detection of adverse events. Patients will require 4 years' continuous practice data.

[figure not shown]

Figure 5: Study Design (database outcomes) extractions from 2005 onwards

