6.2 Inclusion and exclusion criteria (database outcomes)

Inclusion criteria

Diagnosis for asthma (confirmed by diagnostic Read code)

Age ≤65 years at index date for main outcomes, all ages for exploratory

4-years of continuous practice data comprising 1-year baseline data and 3-year outcome data

≥2 separate prescriptions of the beclomethasone pMDI in outcome year after index prescription date

Stepped down ICS in outcome period

Spacer prescription (Aerochamber or Volumatic)

Exclusion criteria

Received multiple types of ICS or FDC ICS/LABA during the baseline period, at the index date or during the outcome period

Prescribed both Aerochamber and Volumatic spacers

Table 7: Inclusion and exclusion criteria for database outcomes

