7.2 Demographics and baseline variables for database outcomes

- Gender (male/female)

* Calculated as average number of puffs per day over the year multiplied by strength (in µg);
i.e. $\frac{\text{Number of inhalers} \times \text{doses per inhaler}}{365} * \text{strength}$

† See appendix 1 for definitions

- Age of patient (years, at index date)
- Body Mass Index (BMI, at time nearest index date, calculated from height and weight data if available, otherwise taken from practice-recorded BMI value, detailed definition in Appendix 1)
- Smoking status (identified by Read code, closest to index date)
- SABA daily dose calculated in baseline prior to index date*
- Percentage predicted peak flow (peak flow predicted, closest to index date)
- Total cumulative ICS dose
- Total cumulative non-extrafine beclomethasone dipropionate therapy
- Duration of ICS therapy
- Number of exacerbations (ATS/ERS 2015 consensus definition[†]) prior to index date
- Number of oral corticosteroid prescriptions prior to index date
- Number of antibiotic prescriptions for lower respiratory tract infections prior to index date
- History of comorbidities related to asthma:
 - Pneumonia (Read code diagnosis in the year prior to the index date)
 - Diabetes (Read code diagnosis and/or antidiabetic drugs ever prior to the index date)
 - Ischaemic heart disease (Read code diagnosis prior to the index date)
 - Rhinitis (Read code diagnosis, including chronic and allergic rhinitis and prescriptions for nasal steroids prior to index date)
 - Eczema (Read code diagnosis prior to index date)
 - Osteoporosis (Read code diagnosis prior to the index date)
 - Charlson Comorbidity Index (based on Read code diagnoses in the year prior to index date, detailed definition in Appendix 1)

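### Index year is not named as a baseline, matching or adjustment variable for the database comparison, although spacer index dates can span about eight years

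*Protocol*

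**What the plan says.** Protocol section 5.4 defines the database design: "The index date is the date of prescription of a spacer", followed by a three-year outcome period. The caption of Figure 5 in that section describes "extractions from 2005 onwards". Section 6.2 requires "4-years of continuous practice data comprising 1-year baseline data and 3-year outcome data". Section 13.0 plans data extraction for 10 November 2016.

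Section 7.2 lists the baseline variables for this design: sex, age, BMI, smoking, SABA dose, peak flow, ICS dose and duration, exacerbations, oral steroid and antibiotic prescriptions, and comorbidities. It contains neither index date nor calendar year, and the mock baseline tables in Appendix 2 have no such row.

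On matching, section 8.3 states: "Matching variables such as demographic data, disease co-morbidity and indicators of disease severity will be considered". Selection combines an analysis of the baseline data with modelling of those data against the primary outcome. Section 4.2.1 defines that outcome as patient-reported thrush or hoarseness. Section 8.4.2 then fits a conditional Poisson model adjusted for baseline confounders that it does not name. The database outcomes in section 7.4 are eight Read-coded diagnoses.

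**The concern.** The database comparison is not randomised, and patients enter it over a long calendar period. Two things may plausibly change over such a period: which spacer is prescribed with this inhaler, and how often an event is recorded as a Read code. Section 3.0 itself notes that Read codes seldom capture some effects that patients report, so recorded rates depend on recording practice.

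If both changed, the spacer used more in later years would collect more (or fewer) coded events for reasons unrelated to the spacer. Giving every patient three outcome years equalises the length of follow-up but not its era. A 1:1 pair can join patients indexed several years apart, and the conditional model removes only what the pair shares.

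The selection rule adds to this. It screens variables on a patient-reported outcome, so a variable that mainly drives Read coding may show no association there and be passed over. At stake is the interpretation of the secondary rate ratio.

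**Working it through.** The protocol gives no figure on this point to reproduce. The check has four steps.

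**1. Index window, database design.** Inputs: records from 2005 (5.4), one baseline year and three outcome years (6.2), extraction on 10 November 2016 (13.0).
- Earliest index: January 2005 + 1 year = January 2006.
- Latest index: November 2016 − 3 years = November 2013.
- Span: 7 years 10 months, about eight years.

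**2. Where index year could enter.** It is not in the 7.2 list, the mock baseline tables or the kinds of matching variable named in 8.3. Section 8.4.2 names no confounder at all. So nothing names it, and nothing excludes it.

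**3. Size under assumed trends, two periods.** Take two equal periods with Aerochamber shares a0 and a1, recorded event rates 1 and r, and no true spacer effect:

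ratio = [(a0 + a1·r)/(a0 + a1)] ÷ [((1−a0) + (1−a1)·r)/((1−a0) + (1−a1))]

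- Shares 0.3 then 0.6, r = 1.25: (1.05/0.9) ÷ (1.20/1.1) = 1.167 ÷ 1.091 = 1.07.
- Same shares, r = 1.5: (1.20/0.9) ÷ (1.30/1.1) = 1.333 ÷ 1.182 = 1.13.
- Shares 0.2 then 0.7: r = 1.25 gives 1.194 ÷ 1.068 = 1.12, and r = 1.5 gives 1.389 ÷ 1.136 = 1.22.

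**4. Size under assumed trends, eight index years.** Take years j = 0 to 7 of equal size, Aerochamber share s_j changing linearly, recorded rate r_j = (1+g)^j, and no true effect:

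ratio = [Σ s_j r_j / Σ s_j] ÷ [Σ (1−s_j) r_j / Σ (1−s_j)]

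| Aerochamber share, first to last year | g = 0 | g = 3% a year | g = 5% a year | g = 10% a year |
|---|---|---|---|---|
| 50% to 50% | 1.000 | 1.000 | 1.000 | 1.000 |
| 40% to 60% | 1.000 | 1.018 | 1.030 | 1.058 |
| 30% to 70% | 1.000 | 1.036 | 1.060 | 1.120 |
| 20% to 80% | 1.000 | 1.055 | 1.092 | 1.186 |
| 10% to 90% | 1.000 | 1.073 | 1.124 | 1.255 |

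Within any single index year both groups have the same rate r_j, so stratifying or matching on year returns 1.00 in every cell. Replacing s by 1−s inverts the ratio. With the share falling from 70% to 30% and g = 10%, for example, it is 1/1.120 = 0.89.

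These are crude ratios, but they bear on the planned model. With 1:1 pairs, equal follow-up and no covariates, the conditional Poisson estimate is total events in one group divided by total events in the other. If the matching variables are unrelated to index year, matching leaves each group's spread of index years unchanged, and the expected ratio is the crude one. If they partly track index year, part of the distortion is removed.

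**The case against.** The strongest objection is that the protocol leaves the covariate set open. Section 8.3 gives examples, not a closed list, and does not cite 7.2 as the only source of candidates. The mock tables include FEV1/FVC ratio, which is in neither baseline list, so the lists are not treated as exhaustive. A final adjustment set is also commonly left to a statistical analysis plan. This stands in part. A reader might infer that the procedure cannot select index year, or that no planned adjustment would remove a time trend; the text supports neither. What remains is that index year is not named, would not appear in the planned baseline comparison, and would not reliably surface from a screen on the questionnaire outcome.

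A reader might also carry the concern over to the primary analysis. The documents do not support that. For the questionnaire design, "The index date of the study is the date of administration of the BLF Questionnaire", no calendar window is given, and Read-coding drift cannot alter a patient's own tick-box answer.

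Nor does the text show that bias is present. It gives no trend in spacer use or coding, so a range that starts above 1.00 would claim too much. The eight-year window itself depends on a caption whose figure is not available here. If 2005 were the first index year rather than the first year of records, the window would be one year longer. With records starting in 2005, the required baseline year rules out a 2005 index.

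Finally, adding a year band to exact and coarsened exact matching thins the cells, and the loss of pairs cannot be calculated from the documents. That counts against matching on year, but not against using it as a covariate.

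**Conclusion.** The point holds as a minor one, for the secondary database comparison only. Index dates there can span about eight years, and the plan names calendar time nowhere as a variable to show, match on or adjust for.

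With no true spacer effect, the spurious crude ratio is 1.00 if either trend is absent, 1.02 to 1.13 under moderate drift (shares moving 40% to 60% or 30% to 70% over eight years, or 30% to 60% between two halves), and about 1.25 under strong drift (10% to 90% with coded events rising 10% a year). It falls below 1 if the trends run in opposite directions. All of these rest on assumed trends, and the actual direction and size are unknown. The case for acting is that the remedy is close to free, not that an error has been shown.

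**What to change.** Add year of index to the section 7.2 baseline list and to the mock baseline tables, and show its distribution by spacer before and after matching. In section 8.4.2, name it as a covariate in the database Poisson model, for example in two- or three-year bands so that no linear trend is imposed.

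The index date defines the cohort and is already held, so no new data are needed. As a covariate it loses no pairs and costs a few model parameters. Matching on coarse year bands is optional and may lose pairs, so decide on it after the distribution by spacer has been seen and before outcomes are compared.
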